## PROTOCOL SYNOPSIS

A Phase 2 Randomized, Placebo-Controlled Study in Mainland China to Evaluate the Safety, Tolerability, Pharmacokinetics and Antiviral Activity of VIR-2218	
Planned to be conducted at multiple clinical investigative sites in mainland China.	
Phase 2	
Up to 30 subjects	
Up to 30 adult subjects with HBeAg-negative or HBeAg-positive chronic hepatitis B virus (HBV) without cirrhosis on nucleos(t)ide reverse transcriptase inhibitor (NrtI) therapy.	
Adult subjects with chronic HBV infection without cirrhosis on NrtI therapy.	
Inclusive of screening to post-dose follow-up, the estimated total time on study for each subject is up to 20 weeks: screening period (4 weeks), dosing period (4 weeks) and post-dose follow-up period (12 weeks).	
Additional HBsAg monitoring is required for subjects with a $\geq 1$ $\log_{10}$ change from baseline (Day 1 predose level) decrease in HBsAg achieved by the Week 16 visit. Subjects will be followed until the HBsAg level returns to $> 90\%$ of the Day 1 predose level or Week 48, whichever comes earlier. Additional HBsAg monitoring may be discontinued at the Sponsor's discretion based on emerging data.	
Post-dose follow-up period:	
All subjects will be followed until Week 16.	
Extended follow-up period:	
Extended follow-up visits will occur every 4 weeks starting at Week 20 and up to Week 48.	

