### **Extended follow-up period:**

Subjects who require additional HBsAg monitoring will return to the clinical investigational site for in-person assessments. Extended follow-up visits will occur every 4 weeks starting at Week 20, and subjects will be followed until the HBsAg level returns to > 90% of the Day 1 predose level or Week 48, whichever comes earlier. Additional HBsAg monitoring may be discontinued at the Sponsor's discretion based on emerging data.

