## 8.3.2. Serious Adverse Events

All SAEs, regardless of cause or relationship, that occur after the subject first consents to participate in the study (i.e., signing the informed consent) and throughout the duration of the study, including the protocol-required follow-up period, must be reported as instructed. This also includes any SAEs resulting from protocol-mandated procedures performed after informed consent is signed.

Investigators are not obligated to actively seek SAEs after the protocol--defined follow-up period. However, if the investigator learns of any SAEs that occur after study participation has concluded and the event is deemed relevant to the use of study drug, he/she should promptly document and report the event to Sponsor.

- For fatal or life-threatening events, copies of hospital case reports, discharge summaries, autopsy reports, and other documents should be submitted by email when requested and applicable. Transmission of such documents should occur without personal subject identification, maintaining the traceability of a document to the subject identifiers.
- Additional information may be requested to ensure the timely completion of accurate safety reports.
- Any medications necessary for treatment of the SAE must be recorded onto the concomitant medication section of the subject's electronic case report form (eCRF) and the event description section of the SAE form.
- Email the SAE form within 24 hours of the investigator's knowledge of the event. Contact information is as follows:

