### 9.5. Safety Analysis

All safety analyses will be performed using the Safety Analysis Set. Safety will be evaluated by assessment of clinical laboratory tests, physical examinations, ECGs, vital signs measurements at various timepoints during the study, and by the documentation of AEs.

All safety data collected up to 12 weeks after the last study drug administration will be summarized by cohort for each VIR-2218 dose and placebo.

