12.1 Adverse Events

12.1.1 *Definition of variables*

- AE
- Serious adverse event (SAE)
- Treatment emergent adverse event (TEAE)

AEs and SAEs are defined in the study protocol. TEAEs are defined as any AEs with an onset date of on or after the study drug start date and no later than 30 days after permanent discontinuation of study drug. If a subject experiences an AE before dosing and after dosing, this AE will be considered as TEAE only if it has worsened in severity. Adverse events that have missing onset dates will be considered treatment-emergent, unless the stop date is known to be prior to the first administration of the study medication. Related AEs are adverse events with relationship as "Related" collected in CRF or missing relationship.

Please refer to section 14 for handling of partial dates for AEs.

12.1.2 *Biostatistical methods*

All AEs will be coded using MedDRA.

AE summary tables will be provided. Summary tables will include the number of subjects (%) experiencing an event and the number of events. Subjects will be counted only once at each SOC and PT level of summary.

The AE, SAE and TEAE summaries will include:

- Overall Summary of all AEs including SAEs
- Overall Summary of TEAEs
- TEAE summary by SOC and PT
- TEAE of Common Terminology Criteria for Adverse Events (CTCAE) Grade ≥ 3 summary by SOC and PT
- Drug related TEAE summary by SOC and PT
- TEAE leading to study withdrawal summary by SOC and PT
- TEAE leading to treatment withdrawal summary by SOC and PT
- Serious TEAE summary by SOC and PT
- Serious TEAE of CTCAE Grade ≥ 3 summary by SOC and PT
- Drug related serious TEAE summary by SOC and PT
- Serious TEAE leading to study withdrawal summary by SOC and PT
- Serious TEAE leading to treatment withdrawal summary by SOC and PT
- SAE summary by SOC and PT
- SAE of CTCAE Grade ≥ 3 summary by SOC and PT
- Drug related SAE summary by SOC and PT

- SAE leading to study withdrawal summary by SOC and PT
- SAE leading to treatment withdrawal summary by SOC and PT
- TEAE leading to death summary by SOC and PT
- Death
- TEAE summary by CTCAE Grade, SOC and PT
- Serious TEAE summary by CTCAE Grade, SOC and PT
- SAE summary by CTCAE Grade, SOC and PT

All AEs will be listed and will include verbatim term, PT, SOC, treatment, severity, causal relationship to the study drug, seriousness, outcome, and action taken with regards to the study drug. Separate listings will be created for AEs leading to study withdrawal and SAEs.

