15. CHANGES TO THE PLANNED ANALYSIS

Not applicable.

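### SAP 12.1.2 sets no upper time limit on its by-arm SAE and death outputs, omitting the protocol's 12-week cut-off although only HBsAg responders are followed beyond Week 16

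*SAP*

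**What the plan says.** **Collection.** Protocol 8.3.2 requires SAEs from consent onwards "throughout the duration of the study, including the protocol-required follow-up period, must be reported as instructed". After that, "Investigators are not obligated to actively seek SAEs after the protocol--defined follow-up period", although an investigator who learns of a later SAE relevant to study drug should still report it. Non-serious AEs stop at 12 weeks after the last dose for everyone (Protocol 8.3.1).

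**Length of follow-up.** The protocol synopsis states: "All subjects will be followed until Week 16". Beyond that, Protocol 4.1 provides: "Subjects who require additional HBsAg monitoring will return to the clinical investigational site for in-person assessments". The trigger is an HBsAg decrease of at least 1 log10 from Day 1 by Week 16. Visits then run every 4 weeks from Week 20 until HBsAg recovers towards its Day 1 level or Week 48, whichever is earlier, and the sponsor may stop them sooner.

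**Analysis.** Protocol 9.5 states: "All safety data collected up to 12 weeks after the last study drug administration will be summarized by cohort", for each VIR-2218 dose and placebo. SAP 12.1.1 limits TEAEs to 30 days after permanent discontinuation. SAP 12.1.2 then lists Serious TEAE tables and, separately, an "SAE summary by SOC and PT". It adds SAE tables for Grade 3 or higher, drug-related, leading to study withdrawal, leading to treatment withdrawal and by CTCAE grade, as well as SAEs within the overall AE summary and a Death output. None of these has a stated window. SAP 3.1 presents all summaries by treatment arm. SAP 16 plans one analysis, after all subjects have completed the study. On changes to the planned analysis, SAP Section 15 says "Not applicable".

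**The concern.** How long SAEs are actively collected depends on a response that the drug is meant to produce. Protocol 1.2.2 says NrtIs do not directly affect HBsAg production, and Protocol 1.2.4 reports notable HBsAg reductions at 50 mg and 100 mg in the regional study. It is therefore reasonable to infer that nearly everyone in extended follow-up will be on VIR-2218. The rule itself is response-based, not arm-based.

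The database behind the single final analysis will include the extended period, and nothing in the SAP removes it from the all-SAE and death outputs. These outputs give subject counts and percentages with VIR-2218 beside placebo. Safety is the primary objective, and the placebo group is very small (4 subjects in the planned cohorts, 6 at most). A single late SAE in a responder could appear as an active-only event with nothing in the table to show that placebo was observed for less time.

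**Working it through.** **1. Durations in the plan.** Screening 4 + dosing 4 + follow-up 12 = 20 weeks, as in the synopsis. Screening 4 + study Week 48 = 52 weeks, as in Protocol 4.1. The second total works only if the 48 weeks given there for extended follow-up mean up to study Week 48; added literally, 4 + 4 + 12 + 48 = 68.

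**2. Maximum imbalance for one subject.** From first dose: 48/16 = 3.0. From last dose: (48 − 4)/(16 − 4) = 44/12 = 3.67. From consent: 52/20 = 2.6. A subject who leaves extended follow-up at Week 20 gives 20/16 = 1.25.

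**3. Arm-level imbalance.** Let q be the share of active subjects who stay to Week 48, with the rest and all placebo subjects leaving at Week 16. The ratio of mean observation from first dose is (16 + 32q)/16. The documents do not give q, so the values below are assumptions.

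| q | Active mean (weeks) | Ratio to placebo |
|---|---|---|
| 0 | 16 | 1.0 |
| 0.25 | 24 | 1.5 |
| 0.50 | 32 | 2.0 |
| 1.00 | 48 | 3.0 |

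**4. Expected excess with no drug effect.** Late SAEs per 100 active subjects = rate per 100 person-years × q × 32/52. The SAE rate is also an assumption.

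| Rate per 100 person-years | q = 0.25 | q = 0.50 | q = 1.00 |
|---|---|---|---|
| 2 | 0.3 | 0.6 | 1.2 |
| 5 | 0.8 | 1.5 | 3.1 |
| 10 | 1.5 | 3.1 | 6.2 |

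The excess is given per 100 subjects because raw counts in 16 active and 4 placebo subjects differ fourfold through the 4:1 allocation alone.

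**5. Chance that any late SAE occurs.** At 5 per 100 person-years, q = 0.50 and 16 active subjects (planned cohorts), the expected number is 16 × 0.5 × 32/52 × 0.05 = 0.246, so P(at least one) = 1 − exp(−0.246) = 0.22. With 24 active subjects (optional cohorts included) it is 0.369 and 0.31.

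**6. Which outputs are exposed.**
- Exposed: the SAE tables (all, Grade 3 or higher, drug-related, leading to study withdrawal, by CTCAE grade), SAEs in the overall AE summary, and Death.
- Not exposed: the TEAE, Serious TEAE and TEAE-leading-to-death tables, which share the 30-day window.
- In effect not exposed: SAE leading to treatment withdrawal. The last dose is at Week 4, so an SAE after Week 16 cannot cause it.

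**7. With the Protocol 9.5 cut-off.** Every subject who receives both doses and completes Week 16 contributes 16 weeks from Day 1, so the ratio is 16/16 = 1.0.

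**The case against.** The strongest reply is that the protocol already settles the matter. The SAP takes its AE and SAE definitions from the protocol, names Amendment 2 as its reference and declares no changes, so its silence may mean that the Protocol 9.5 limit applies. That stands to this extent: the imbalance arises only if the SAP is programmed as written, and no deliberate departure is shown. It does not remove the point. The SAP states a 30-day window for one family of tables and none for a parallel family, and a programmer has no instruction to supply 12 weeks.

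The other replies narrow the point:
- A reader might infer that active columns will carry three times the observation of placebo. Threefold is the ceiling from first dose, reached only if every active subject responds and stays to Week 48. Recovery of HBsAg or a sponsor decision can end follow-up sooner.
- A reader might infer that the tables will show more SAEs and deaths on VIR-2218, or a false dose-related harm. Only a small expected excess follows, and cohorts of 4 active subjects cannot support a prediction about dose pattern.
- A reader might infer that the primary endpoint is biased. TEAE incidence uses an equal 30-day window, no hypothesis test is planned, and SAEs are listed by subject.
- Week 16 is not an absolute stop. Later SAEs judged relevant to study drug are reportable in any subject if the investigator learns of them, so the asymmetry is weaker for the drug-related SAE table.
- Tabulating every SAE is a defensible full accounting. It then needs to be declared and adjusted for follow-up time.

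**Conclusion.** The point holds as a gap between SAP 12.1.2 and Protocol 9.5 with a specific consequence. Followed literally, the SAP's all-SAE and death outputs compare VIR-2218 with placebo over response-dependent observation: at most 48 versus 16 weeks for one subject, and 1.5 to 3.0 at arm level if 25% to 100% of active subjects stay to Week 48.

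The expected effect is small. At an assumed 5 SAEs per 100 person-years with 50% staying, it is about 1.5 SAEs per 100 active subjects, and in most runs of the planned cohorts (78%) no late SAE would occur. The responder share, time in extended follow-up and SAE rate are all assumptions, and the concentration of responders in the active arm is an inference from mechanism and regional data. The change is still worth making, because it prevents an avoidable differential-follow-up bias in outputs that serve the primary objective.

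**What to change.** In SAP 12.1.2, state that by-arm SAE and death summaries, including SAEs in the overall AE summary, use the Protocol 9.5 cut-off of 12 weeks after the last dose. List SAEs and deaths with later onset separately, with the number of subjects and the follow-up time per arm.

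If the sponsor prefers to tabulate all SAEs whenever they occur, declare the change in SAP Section 15 and report exposure-adjusted rates.

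The first option costs a few lines of SAP text, one date filter and one listing. It needs no new data and no protocol amendment. Its small downside is that late SAEs move from the main tables to a listing, where they remain visible.

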12.2 Safety Laboratory Assessments

Blood and urine samples will be collected at the time points specified in the Schedule of Assessments (refer to the protocol) to conduct hematology, chemistry, liver function tests, coagulation, urinalysis, pregnancy testing, and serology analyses.

The following tests will be performed within each of the specified test panels:

Hematology:

- Complete blood count with differential

Chemistry:

- Albumin
- Creatinine clearance
- Blood urea nitrogen (BUN)
- Gamma glutamyl transferase (GGT)
- Calcium
- Glucose
- Carbon dioxide/bicarbonate
- Lactate dehydrogenase (LDH)
- Chloride
- Potassium
- Creatine kinase
- Sodium
- Creatinine
- Uric acid

Liver Function Tests:

- Alkaline phosphatase (ALP)
- Aspartate aminotransferase (AST)
- Alanine aminotransferase (ALT)
- Bilirubin (total and direct)

Coagulation:

- International normalized ratio (INR) time
- Prothrombin

Urinalysis & Microscopic Urinalysis:

- Bilirubin
- Proteins
- Glucose
- Red Blood Cells
- Ketones
- Screen for drugs of abuse
- Leukocytes
- Specific gravity
- Microscopy (if clinically indicated)
- Urobilinogen
- Nitrite
- Visual inspection for appearance and color
- pH

Pregnancy Testing:

- Beta-human chorionic gonadotropin (WOCBP)
- Urine pregnancy test

Serology

- Hepatitis B, C, and Delta
- Human immunodeficiency virus I and II

12.2.1 Biostatistical Methods

All laboratory data collected at scheduled and unscheduled visits will be included in the listings, but only results collected as scheduled visits will be included in the summary tables. Repeated and unscheduled assessments will be included in the derivation of the baseline values and minimum/maximum values post baseline. All information will be presented by cohort and study part.

Results for individual parameters may be reported in different units depending on the analyzing laboratory. If required, the results (and the corresponding normal range cut-off values) for individual parameters may be converted to International System of Units (S.I.) units to summarize the data.

For all the parameters where a unit value has been reported, the parameter names that will be used in the outputs will comprise the test name and the unit of measure, for example, 'Albumin (g/L)'. Parameters will be sorted alphabetically within tables and listings.

For all parameters where a normal range limit value is reported, the normal range will be derived based on the available lower and upper limit values and any reported mathematical symbols. If both a lower and upper limit value is available, the normal range will be presented as '(Lower, Upper)'.

The reported results for each parameter with a defined normal range will be classified ('Low', 'Normal' or 'High') in relation to the defined normal range limits. If a result is equal to the normal range cut-off value, the result will be considered normal.

The change from baseline values at each post-baseline visit will be calculated for all parameters with continuous results.

The minimum/maximum post baseline value will be the minimum/maximum non-missing value after baseline and during the reference period. Scheduled visits, unscheduled visits, and repeated measurements will be included to derive the minimum/maximum post baseline values.

The decimal precision to which the summaries for each parameter will be based on the maximum number of decimals to which the reported result or the normal range limits are presented to in the raw data. The results and normal ranges will be displayed to the same decimal precision in the listings.

The hematology and chemistry results tables will present summary statistics for each laboratory parameter within the specific test panel. For each parameter, summaries will be presented for the baseline and each scheduled post-baseline visit. In addition, summaries will be presented for the change from baseline values at each scheduled post-baseline visit.

The incidence of treatment-emergent laboratory abnormalities, defined as values that increase at least 1 toxicity grade from baseline at any postbaseline timepoint will be summarized by cohort.

The worst post baseline value will be the worst non-missing value after baseline and during the reference period. Scheduled visits, unscheduled visits, and repeat measurements will be included to derive the worst post baseline values.

Additionally, shift tables from baseline in CTCAE grade (version 5) by visit plus worst post-baseline will be summarized by counts and percentages.

The urinalysis table will present counts and percentages for the reported results at baseline and each post-baseline visit within each test parameter. Result categories will be order alphabetically, or in ascending order.

The listings of laboratory parameters will include all the information (fields) collected (including CTCAE derived values). In addition, the observations that are used as the baseline record (value) for each parameter will be flagged, and the change from baseline values at each post-baseline visit will be presented.

12.3 Vital Signs Measurements

The following vital signs measurements will be taken at the time points specified in the Schedule of Assessments (refer to the protocol):

- Systolic blood pressure (SBP) (mmHg)
- Diastolic blood pressure (DBP) (mmHg)
- Pulse rate (beats/min)
- Respiratory rate (breaths/min)
- Temperature (°C)

12.3.1 Biostatistical Methods

All vital signs data collected at scheduled and unscheduled visits will be included in the listings, but only results collected as scheduled visits will be included in the summary tables. Repeated and unscheduled assessments will be included in the derivation of the baseline values and

minimum/maximum values post baseline. All information will be presented by cohort and study part.

The parameter names that will be used in the outputs will comprise the test name and the unit of measure, for example, 'Systolic Blood Pressure (mmHg)'. Parameters will be sorted in the order that the measurements were collected in on the Vital Signs eCRF page within the tables and listings: Systolic Blood Pressure, Diastolic Blood Pressure, Pulse Rate, Respiratory Rate, and Temperature.

The change from baseline to the pre-dose assessment at each post-baseline visit will be calculated for all parameters. If unscheduled pre-dose assessments are recorded on Day 1, the average of the pre-dose Day 1 and unscheduled pre-dose assessments will be used as baseline for all change from baseline calculations.

The minimum/maximum post baseline value will be the minimum/maximum non-missing value after baseline and during the reference period. Scheduled visits, unscheduled visits, and repeat measurements will be included to derive the minimum/maximum post baseline values.

The decimal precision to which the summaries for each parameter will presented will be based on the maximum number of decimals to which the results were reported on the eCRF.

Vital signs measurements will present summary statistics for the results at the baseline and each scheduled post-baseline visit for each of the parameters. In addition, summaries will be presented for the change from baseline values at each scheduled post-baseline visit.

The listings of vital signs measurements will include all the information collected. In addition, the observations that are used as the baseline record (value) for each parameter will be flagged, and the change from baseline values at each post-baseline visit will be presented.

12.4 12-Lead Safety Electrocardiogram (ECG)

12-lead safety ECGs interpretations will be recorded and reviewed on-site by the investigator as outlined in the Schedule of Assessments (refer to the protocol). This 12-lead safety ECGs will be measured in the supine position after the subject has rested comfortably for 10 minutes.

12.4.1 Biostatistical Methods

All ECG data collected at scheduled and unscheduled visits will be included in the listings, but only results collected as scheduled visits will be included in the summary tables. All information will be presented by cohort and study part.

The summary of overall interpretation findings table will present counts and percentages for the reported results at baseline and each post-baseline visit/time point. Result categories will be ordered as 'Normal', 'Abnormal - Not Clinically Significant (NCS)' and 'Abnormal - Clinically Significant (CS)'.

The worst post baseline value will be the worst non-missing value after baseline and during the reference period. Scheduled visits, unscheduled visits, and repeat measurements will be included to derive the worst post baseline values (Abnormal CS is the worst, Abnormal NCS is next, then normal).

Additionally, shift tables from baseline in categories as 'Normal', 'Abnormal - Not Clinically Significant (NCS)', 'Abnormal - Clinically Significant (CS)' and 'Missing', will be summarized by counts and percentages.

The listings of ECG measurements will include all the information collected. In addition, the observations that are used as the baseline record (value) for each parameter will be flagged, and the change from baseline values at each post-baseline visit will be presented.

